CIN. Target heart rate (THR) using the 60% to 70% of maximum HR achieved on the cardiopulmonary exercise test (CPET) will be used to monitor the intensity and training response for aerobic exercise. Each participant will be provided with an individualized THR zone based on CPET results.¹⁰⁷ Under the supervision of a research nurse, participants will begin the walking sessions at 60% of THR and increase to 70% by week 5 as shown in Table 2. In our pilot with HF patients, a progressive moderate intensity level exercise program yielded positive outcomes with no adverse events, was appealing to participants and adherence rates were 80% or higher.

Group 2: EX/CT (UC + aerobic exercise + cognitive training) The first 2 weeks of the study will consist of 2 consecutive weekly home visits by the research nurse to demonstrate use of the HR monitor, pedometer and the CT program, Brain Fitness (Posit, San Francisco, CA detailed below). The research nurse will supervise one walking session during the first 2 weeks to ensure the safety of the participant and that he/she understands how to use the Polar HR monitor and pedometer and how to complete the walking logs. During the first 2 weeks, the research nurse will also provide training and demonstrate how to use the Brain Fitness computerized cognitive training program designed to be completed in 40 sessions over 12 weeks. We expect that participants will require additional time (at least 30 minutes each time) in the first 2 weeks to learn how to use and access the Brain Fitness program. The weekly schedules are provided in table 1.

The weekly schedules are provided in table 1.

Brain Fitness Computer Training: is based on the principles of positive brain plasticity and designed for use by adults. The training program (“Brain Fitness”) is focused on speech reception to strengthen an individual’s memory for speech. It has 6 modules names Hi-Lo, Tell Us Apart, Match It, Listen and Do, Sound Replay and Story Teller. Research to date has found: 1) participants with limited or no computer experience were capable of learning to perform the training exercises, 2) the training was safe and well tolerated by participants, and 3) healthy participants who trained on Brain Fitness showed on average a 1/3 standard deviation of improvement in memory, concentration and cognition, and 4) it has been tolerated well in patients in HF in a prior study.¹⁶

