Group 3: Ex only group (UC + aerobic exercise). The same exercise protocol will be used as above without the computer training.

Exercise adherence. To be 100% adherent for exercise sessions, participants in both groups 2 and 3 must document walking weekly at the prescribed intensity/duration on the exercise log. Participants will record on a calendar provided: maximum HR achieved; rate of perceived exertion (RPE) during walk; and number of steps walked during the walking sessions. Polar HR monitors and pedometers (described in instruments) will be used to objectively document exercise intensity (i.e., maximum HR and RPE achieved), duration, walking adherence and progression. The Polar HR monitor and pedometer data will be downloaded during each home visit during the first 2 weeks to track exercise duration and steps walked. At T2, data collected from the HR monitors and pedometers will also be downloaded to document exercise adherence. A total summary adherence score will be calculated by summing and dividing weekly adherence scores by total number of weeks walked.

CT adherence. The total number of minutes for the full Brain Fitness program is approximately 2400 minutes over 8 weeks. Patients will be considered adherent if they meet or exceed 80% of the required minutes for the intervention. Total number of minutes can be accessed from the program to monitor adherence.

VARIABLES, DEFINITIONS AND MEASURES. Variables, operational definitions and methods are described below and in Table 3. Questionnaires will be administered at the time of the visit by a trained research assistant blinded to group allocation. Core services and Center activities will greatly enhance the success of this study. Through training and monitoring in administration and scoring of the core test battery, regular consultation with the BMC to monitor implementation issues, systematic data management and analysis, and support in using these findings to prepare an RO1 application, this study will achieve its aims and further the goals of this Center.

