Rationale for sample characteristics. The age range was selected to avoid confounding effects of age and sarcopenia with outcomes such as aerobic capacity, BDNF and HRQOL; participants below the age of 40 years are likely to have HF for other reasons than the majority of the general HF population. Older age (>75) is associated with reduced exercise capacity and age related cognitive decline which may confound physical function cognitive outcome measurement. In addition, persons over the age of 75 are at higher risk for adverse events during exercise testing and with aerobic exercise. Although we anticipate most participants to be receiving optimal medication therapy, treatment decisions regarding individual care will be based on patient's clinician; evidence-based care will be encouraged. If any participants are not being treated with what is considered optimal medication therapy according to ACC guidelines, the reason (eg, intolerance) will be recorded and tracked by group and statistically controlled as a covariate. We recognize that both resting and exercise heart rates are influenced by beta-blockers, which is considered optimal therapy for HF patients. For both exercise testing and training we will use the heart rate reserve method which takes into account the patient's resting heart rate, thereby reducing the effect of beta-blockade. We will attempt to schedule patients for their exercise testing and training a minimum of 3 hours after taking beta blockers.²⁸⁻²⁹ For patients who are unable to schedule exercise during this time frame or exercise up to the prescribed heart rate, Borg's 6-20 rate of perceived exertion scale (RPE) between 12-15, will be used to guide exercise intensity, consistent with a moderate intensity level exercise. Patients with an ICD may be enrolled if their heart rate limits are set to be higher than the target heart rate for the exercise regimen. In our last preliminary study, approximately 90% had an ICD; there were no firings during exercise or any increase in adverse events. Although unlikely to occur, participants with a fixed rate pacemaker would not be able to participate because heart rate may be set at a lower rate than required to achieve prescribed target heart rate. Participants who have recurrent angina, more severe symptoms have uncontrolled hypertension will be excluded due to the higher risk for adverse cardiovascular events during exercise testing and the walking intervention. Because moderate to severe depressive symptoms are a major predictor of exercise attrition and more severe CI, participants will be excluded who have a BDI-II score of 25 or higher. These severely depressed subjects will be evaluated for suicidal risk, and referred to psychiatric care. Because the benefit of exercise is being evaluated, participants who are currently enrolled, or were recently enrolled in an exercise program for the past 8 weeks, currently exercising at regular intervals (more than twice per week for 30 minutes) will not be eligible for the study.

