The potential risks associated with the walking intervention are anticipated to be minimal. Any potential cardiovascular (CV) events that poses risk to the participant is anticipated to be detected during the modified Balke maximal treadmill test. In addition, the duration of walking will be limited to 30 minutes during the first 2 weeks and at an intensity level (60%) that is not likely to result in any adverse CV events; if necessary participants can rest as needed until the 30 minute duration of walking is completed. Participants will wear a Polar HR monitor so that HR and intensity level can be closely monitored. Participants will undergo 2 supervised walking sessions prior to walking at home unsupervised; the risk associated with the unsupervised session therefore, is anticipated to be minimal. Participants in the study will be provided with detailed instructions on self-monitoring HR, BP and symptoms associated before, during and after walking. Each participant will be provided with a target heart rate range to stay within during the study period. Participants will be instructed to wear the Polar HR monitor during each exercise session. The participants will take their HR, and BP (if machine available) and weight prior to and after each walking session and record it in their walking calendar. Participants will be instructed to call the research nurse if their BP or HR is outside their normal range. If participants are symptomatic, experience increased shortness of breath or have a greater than 2 pound weight gain over the previous 24 hours, they will be instructed not to exercise. The participants will be instructed to take their medications as usual prior to exercise and instructed on proper attire for exercising. Demonstrations and return demonstrations of the Polar HR monitor will ensure they know how to wear the monitor around the chest as well as trouble shoot when the monitor does not display a HR. They will be instructed that if their HR approaches within 5-10 beats of the target HR range to slow the walking pace down. They will also be instructed if they have an ICD, to keep their HR 15 beats below the firing range at all times (usually set at higher than 170 beats per minute, so it is unlikely to interfere with training stimulus). In addition, they will be instructed to monitor their RPE using the Borg 6 to 20 scale, and to keep their RPE at 12-13 during the initial weeks and to gradually progress with instructions to 15 as stipulated in the protocol. Participants in the intervention groups will be advised to carry a cell phone when they walk at home in the event of an emergency or sudden event. Specifically, participants will be instructed to slow their pace if their HR increases to near THR as previously noted or if they become short of breath. Participants who have ischemic heart disease and prescribed nitroglycerin (NTG) will be instructed to carry their NTG with them during each walking sessions. If chest pain occurs during exercise, the participants will be told to stop exercising and to take a NTG as directed by their cardiologist. The participant will also be instructed if the chest pain continues to sit down and to call a relative or friend and to take another NTG if the chest pain does not subside. If the chest pain continues and is not relieved by NTG within 10 minutes they will be instructed to call 911. If the participant becomes moderately to severely dyspneic where they cannot talk while walking they will be instructed to stop walking until the dyspnea subsides. If the dyspnea continues once they have stopped walking for several minutes they will be instructed to call a relative or friend; if not dissipated they will be

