
instructed to go the nearest emergency room. If a participant becomes dizzy while walking they will be asked to sit down and to get up slowly once the dizziness passes. If an ICD fires, the participant will be instructed to call 911 if symptoms are present; to notify their cardiologist if no symptoms for possible evaluation. In our preliminary work, 90% of participants had an ICD and there were no ICD shocks using a very similar protocol. If symptoms are present at current intensity level or duration of walking the participant will not be progressed until exercising at current level with RPE at 15 or below for 45 minutes. This will better ensure the participant is not progressed too rapidly.

The potential risk to participants in the CT is anticipated to be minimal. Participants will be taught how to use the computerized CT program by a research nurse. It is possible that some participants may have additional stress or anxiety related to participation in the CT. The 2 home visits that will be used to review the CT program are anticipated to alleviate any unusual stress or concern about participation in CT. In addition, the research nurse will be contacting the participant on a weekly basis to discuss any concerns or issues related to CT from weeks 3-12. In a prior study that used the same CT program in persons with HF, Brain Fitness (Posit, San Francisco, CA), there were no adverse events, and satisfaction and adherence were reported to be high.¹⁶

The potential risk to participants in the AC control stretching/flexibility movement group is anticipated to be minimal. Participants will be taught how to use stretching and flexibility movements by a research nurse who is not involved with the intervention groups. In our preliminary work, participants enjoyed this placebo exercise, but it was not strong enough to influence outcomes. Although some participants did experience a better QOL from contact with the research team but this was not as strong as the intervention, and it was of shorter duration.

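### The exercise adherence score does not say how weeks held back, sessions withheld or sessions guided by perceived exertion count, so it can be too low or too high

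*Combined protocol and SAP*

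**What the plan says.** The schedule is common to both exercise arms (C. Approach, Groups 2 and 3 Exercise Prescription, Table 2): three sessions a week for 12 weeks, 30 minutes in weeks 1-2 and 45 minutes after that. On intensity, "participants will begin the walking sessions at 60% of THR and increase to 70% by week 5 as shown in Table 2".

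The scoring rule is in C. Approach, Exercise adherence: "To be 100% adherent for exercise sessions, participants in both groups 2 and 3 must document walking weekly at the prescribed intensity/duration". The summary score comes from "summing and dividing weekly adherence scores by total number of weeks walked". The weekly score itself is not defined. The monitors and pedometers are meant to "objectively document exercise intensity (i.e., maximum HR and RPE achieved), duration, walking adherence and progression".

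Three provisions in E. Human Subjects Research take a compliant walker off the schedule:

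- **Held back** (Potential Risks, walking intervention): "If symptoms are present at current intensity level or duration of walking the participant will not be progressed until exercising at current level".
- **Withheld** (same section): this applies to participants who are symptomatic, are more breathless, or "have a greater than 2 pound weight gain over the previous 24 hours, they will be instructed not to exercise".
- **Guided by exertion** (Rationale for sample characteristics): for those who cannot fit sessions around beta-blocker timing or cannot reach the heart rate, a "rate of perceived exertion scale (RPE) between 12-15, will be used to guide exercise intensity".

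Neither section refers back to the adherence score, and the score does not mention them.

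**The concern.** The scoring rule does not say whether the prescribed level is the one in Table 2 for that week or the one at which the participant is currently held. It also does not say what happens to a session that the protocol told the participant to skip. Whoever computes the score will have to decide, possibly with the data in view.

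Adherence has real work to do here. Aim 1 is feasibility. The paragraph on combined exercise and CT (A. Significance) lists adherence among the things to be evaluated and plans to look for dose responses across levels of compliance. The Adherence paragraph under Variables, Definitions and Measures brings actual adherence into an intent-to-treat analysis. Holds and withheld sessions fall on symptomatic participants. If they lower the score, low adherence is partly a marker of illness, and any relation between adherence and outcome is confounded by it. For the next trial, people who would not walk and people who could not tolerate the walking call for different changes, and one score does not separate them.

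**Working it through.** The plan gives no expected exercise adherence score, so there is no figure to reproduce. The pilot rate of 80% or higher cannot be checked because its scoring method is not given.

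**Inputs.** From Table 2: 60% in weeks 1-4, 70% in weeks 5-12, and 3 sessions × 12 weeks = 36 sessions. From the Exercise adherence paragraph: score = sum of weekly scores ÷ weeks walked.

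**Assumption.** A week scores 1 if all three sessions meet the prescribed level and 0 otherwise. The plan does not state this.

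**The score under the present rule**

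| Participant follows every instruction and... | Prescribed = Table 2 | Prescribed = level in force |
|---|---|---|
| is held at 60% in weeks 5-6, then moves to 70% | 10/12 = 83% | 12/12 = 100% |
| is held at 60% in weeks 5-12 | 4/12 = 33% | 12/12 = 100% |
| has one session withheld in each of 6 weeks | 6/12 = 50% | 6/12 = 50% |
| has 6 whole weeks withheld | 6/6 = 100% | 6/6 = 100% |

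**Sensitivity to the weekly score.** Suppose a week scores the share of its three sessions that meet the level. The two held cases do not change, because no session in a held week reaches 70%. The third row becomes (6 × 1 + 6 × 2/3)/12 = 10/12 = 83%. A rule giving part credit for a session below the scheduled intensity would raise the held scores.

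**The denominator.** The last row does not depend on the reason for not walking. A participant who simply declined to walk for six weeks also scores 6/6 = 100%; over all 12 weeks the figure would be 6/12 = 50%.

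**The same participants on two session-based figures.** Adherence = sessions completed at the level in force ÷ scheduled sessions not withheld on instruction. Delivered dose = sessions completed at the scheduled level ÷ 36.

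| Participant | Adherence | Delivered dose |
|---|---|---|
| Held in weeks 5-6 | 36/36 = 100% | 30/36 = 83% |
| Held in weeks 5-12 | 36/36 = 100% | 12/36 = 33% |
| One session withheld in each of 6 weeks | 30/30 = 100% | 30/36 = 83% |
| 6 weeks withheld on instruction | 18/18 = 100% | 18/36 = 50% |
| 6 weeks declined | 18/36 = 50% | 18/36 = 50% |

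The last two participants both score 100% under the present rule. The pair of figures separates them.

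**The case against.** The strongest reply is that a participant held at a level has, in effect, been prescribed that level. Target zones are individualized from the exercise test, and the hold is expressed in terms of the current level. On that reading a held participant scores 100%. The reading is fair, but the text does not settle it. It leans the other way: one schedule is given as the prescription for both arms, and the Rationale section describes some participants as unable to reach the prescribed heart rate, which treats the prescription as fixed.

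Other parts of the reply stand:

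- Holds are meant to be temporary. The 33% case is an extreme, and a short hold costs much less.
- Exercise has no adherent/non-adherent cut-off. The 80% threshold in the adherence rules applies to CT minutes only, so the effect is a lower score and not a classification.
- Perceived exertion is logged and named as a record of intensity achieved. A reader might infer that participants guided by exertion would fail every week on heart rate; the documents do not support that. What is missing is only a rule for when exertion replaces heart rate in the score.
- Barriers to adherence are collected at visits and calls, and a nurse telephone log is listed as an adherence source. Tolerability is therefore not invisible, although the score itself does not separate it, and the calendar items listed in the plan include no reason for a held or missed session.

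**Conclusion.** The gap is real and should be closed. The same obedient participant can score 33% or 100%, or 83% or 100% after a two-week hold, depending on a definition that the plan does not give. A participant who walked in only half the weeks can score 100%. The held-back figures assume the Table 2 reading and no part credit for sessions below the scheduled intensity. The 6/6 result follows from the stated denominator if the weeks that were walked were fully compliant.

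A reader might infer that following a safety instruction always counts as non-adherence. The documents do not say so. That outcome depends on one reading of an undefined term, and for whole weeks withheld the stated denominator works in the opposite direction. The plan gives no frequency for holds, withheld sessions or exertion-guided walking, so the effect on an arm's mean adherence cannot be estimated from it.

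**What to change.** In the Exercise adherence paragraph, replace the single score with two figures from the same data:

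1. **Adherence**: sessions completed at the level in force for that participant (the held level, or perceived exertion where the Rationale section applies it), divided by scheduled sessions not withheld on protocol instruction.
2. **Delivered dose**: sessions completed at the scheduled level, divided by the 36 scheduled. This removes the weeks-walked denominator.

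State whether an exertion-guided session counts toward delivered dose. Add one field to the walking calendar or nurse log (held, withheld, exertion-guided) and report these counts for each exercise arm as tolerability results. Say which figure enters the dose-response work and the intent-to-treat analysis. Set the definitions before any scoring and add the field before sessions are logged, because reasons are hard to recover afterwards.

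The cost is one extra field, which the weekly calls can help complete, and two reported figures instead of one. The holding, stopping and exertion rules stay as they are.

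Two inconsistencies bear on what the prescribed level means and must be reconciled by the investigators. Release from a hold refers to 45 minutes, while weeks 1-2 are set at 30 minutes. Target heart rate is a percentage of maximum heart rate in the exercise prescription, but uses heart rate reserve in the Adherence and Rationale paragraphs.

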confounding variable of receiving attention from a healthcare professional. Instruction on stretching and flexibility movements is also expected to reduce attrition and patient dissatisfaction and to better ensure concealment of group allocation. These time-equivalent, flexibility/stretching movements have been previously piloted and will serve as the “placebo exercise condition.” In pilot evaluations they were well received, but were not strong enough to influence outcomes. The AC education placebo component will be delivered as soon as feasible after baseline (T1). The first 2 weeks of the intervention phase will include 2 home visits to demonstrate stretching and flexibility movements and to discuss educational materials. Weekly telephone calls will then be made for the next 10 weeks to discuss educational materials and to answer questions about stretching movements. An appointment will be made for participants to come to the ACTSI to collect T2 measures; this will occur at weeks 13 and 14. From weeks 15-24 bi-monthly telephone contact will be used to encourage continued adherence to the AC intervention. At the end of 24 weeks, a final visit to the ACTSI will be arranged and T3 measures will be taken. For ethical and cardiovascular health reasons, the AC group will be advised to exercise, but will not be provided with an exercise prescription or self-monitoring equipment since these have been shown to influence exercise adherence and exercise self-efficacy and may confound study outcomes.¹⁰⁴⁻¹⁰⁵

Groups 2 and 3 Exercise Prescription. Groups 2 & 3 will receive the same exercise prescription using a progressive moderate intensity aerobic protocol. To ensure that participants achieve adequate training stimulus, dose-specific exercise will be based on maximum heart rate (HR) obtained during symptom limited, modified Balke treadmill tests¹⁰⁶⁻¹⁰⁷ conducted by an exercise physiologist and supervising cardiologist in the

	Wk 1-2	Wk 3-4	Wk 5-7	Wk 8-9	Wk 10-12
Intensity	60%	60%	70%	70%	70%
Duration	30 mins	45 mins	45 mins	45 mins	45 mins
Frequency	3 x/wk	3 x/wk	3 x/wk	3 x/wk	3 x/wk

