The PI will assume responsibility for developing and implementing the data and safety monitoring plan. This study is considered to present minimal risks to participants. Adverse events, that is, unfavorable or unintended symptoms temporarily associated with the intervention or evaluation, are expected to be minimal. Possible mild adverse events could include shortness of breath, fatigue, chest pain, dizziness, or rapid beating heart beat during the symptom limited modified Balke treadmill test and muscle strength testing. Subjects will

be informed of these and will be asked to notify the research staff if any of the symptoms occur; they will also have telemetry in place during the tests to detect any heart rhythm changes, blood pressure will be monitored as well before and after these tests. The risks for the adverse events during the home based walking and resistance intervention are also anticipated to be minimal. If symptoms occur during the home-based intervention, participants will be counseled on ameliorating strategies and asked to contact their provider. Before the modified Balke, all participants will receive a brief history and physical by a cardiology fellow or advanced practice nurse, and will be asked if they feel well enough to perform the test. If they experience any untoward symptoms, the treadmill test or muscle strength testing will be stopped and the participant seated and evaluation of symptoms performed by the ACTSI, nursing research team member or study cardiologist. If symptoms persist, the person will be taken to the Emergency Department for further evaluation and treatment. All adverse events will be reported to the IRB, ACTSI and DSMB for review.

The research team will meet periodically to review screening, enrollment and randomization data and to identify any human subject issues that arise. All staff will be trained in the protection of human subjects according to university and NIH regulations, and will be required to be certified in human subject's research in accordance with the Emory University IRB procedures. We will conduct random and periodic audits of research records to ascertain that informed consents are signed, witnessed and complete for each subject, and that confidentiality procedures are being maintained.

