The DSMB will meet with the PI and study team at the beginning of the trial, after 30 patients have been enrolled and completed the study, as well as annually or as needed to review the conduct of the trial, including accrual, recruitment and retention, violations in protocols, adverse events, breaches in confidentiality, or other data related to protection of human subjects. The first meeting of the DSMB will review and make recommendations about consent procedures, and situations within which confidentiality may be broken, for example, if a participant indicates suicide tendencies on the BDI-II. The primary role of the DSMB will be to ensure data integrity and the safety of participants. They will have the power to recommend termination of the trial if significant negative trends emerge. In the highly unlikely event that serious risks occur, they will also have the power to recommend termination of the trial. In addition, study recruitment, and retention procedures will be examined for timeliness, practicality, safety, and protection of all human subjects.

At subsequent regular annual meetings, the DSMB will review adherence to the goals for recruitment and retention; adherence to study protocols; cumulative data for evidence of study related adverse events; quality, completeness, and timeliness of the data collected; factors that could affect the outcome or compromise participant/data confidentiality; and other factors outside the study (e.g., therapeutic developments, agency related policies) that could impact the safety of participants or the ethical conduct of the study. General recommendations the DSMB may include these: continuation of the study without change; modifications to the study protocol; suspension or early termination; alternative approaches to consider. Formal minutes and reports of the DSMB will be maintained and made available to NIH as required. All materials, discussions and reports of the DSMB are considered confidential and will be treated as such in the maintenance of records.

Literature Cited

1. Alosco, M. L., Spitznagel, M. B., Cohen, R., Sweet, L. H., Colbert, L. H., Josephson, R (2012). Cognitive impairment is independently associated with reduced instrumental activities of daily living in persons with heart failure. *J Cardiovasc Nurs* 27(1), 44-50.

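### The adverse-event definition covers only symptoms tied to the intervention or an evaluation, and no stated step brings ICD shocks, emergency visits or hospitalisations at home to the study and its DSMB

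*Combined protocol and SAP*

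**What the plan says.** **Definition.** The Data and Safety Monitoring Plan, in section E (Human Subjects Research), states: "Adverse events, that is, unfavorable or unintended symptoms temporarily associated with the intervention or evaluation, are expected to be minimal". Everything that meets this definition goes to the IRB, the ACTSI and the DSMB. Subjects are asked to tell research staff about symptoms, but that request follows a list of symptoms expected at the treadmill and strength tests. Symptoms during the home programme have their own rule: "participants will be counseled on ameliorating strategies and asked to contact their provider".

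**Home events.** The Potential Risks text on the walking intervention says of chest pain: "If the chest pain continues and is not relieved by NTG within 10 minutes they will be instructed to call 911". Breathlessness that does not settle leads first to a relative or friend and then to an emergency room. For a shock: "If an ICD fires, the participant will be instructed to call 911 if symptoms are present; to notify their cardiologist if no symptoms". One instruction does name the study: "Participants will be instructed to call the research nurse if their BP or HR is outside their normal range".

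**Contacts.** All three arms have two home visits, weekly calls in weeks 3-12, bi-monthly calls in weeks 15-24, and the T2 and T3 visits. For attention control the plan says: "Weekly telephone calls will then be made for the next 10 weeks to discuss educational materials and to answer questions about stretching movements". In the combined arm, the weekly calls are described as covering concerns about the cognitive training.

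**Oversight.** The DSMB's annual review includes "cumulative data for evidence of study related adverse events". The description of its other meetings refers to adverse events without that qualifier. A fuller monitoring plan is still to be developed under IRB and ACTSI guidelines.

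**The concern.** The definition is narrower than the risks the protocol itself describes. Walking at home is largely unsupervised, and that is where the gravest events have no stated path back to the study.

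The DSMB may recommend stopping the trial if negative trends emerge, but it can act only on what is collected. Nobody can judge whether an event is study related if it was never recorded. Participants are enrolled because of cognitive impairment, so unprompted later recall is a weak safeguard. The trial is also meant to inform a larger one in the same kind of patient.

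**Working it through.** This is a check of the text. The documents give no adverse-event rate and no safety sample size, so there is no figure to reproduce.

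**1. Definition against listed risks.** The treadmill risk paragraph names at least four events that are not symptoms or can occur without any: sudden death, arrhythmia, ICD firing and ischaemia on ECG. The walking-risk text separately provides for a shock without symptoms. Read literally, the definition leaves these out. The word *temporarily* may be a slip for *temporally* (an assumption). On either reading the definition covers only symptoms linked to the intervention or an evaluation, so the point does not depend on that word.

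**2. Where each home event goes.**

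| Event | Stated route | Fits the symptom definition? | Step to inform the study |
|---|---|---|---|
| Heart rate or BP out of range (walking arms) | Research nurse | Not in itself | Yes |
| Chest pain not relieved | 911 | Yes | None stated |
| Persistent dyspnoea | Relative or friend, then emergency room | Yes | None stated |
| ICD shock with symptoms | 911 | The symptoms do | None stated |
| ICD shock without symptoms | Cardiologist | No | None stated |
| Other symptoms in the home programme | Counselling (by whom is not said) and own provider | Yes | None stated |
| Hospitalisation or death | Not addressed | No | None stated |

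Of the three serious home pathways (chest pain, dyspnoea, shock), 0 of 3 end with the study being told. The lesser signal does have a route.

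**3. Active collection.** Weeks 3 to 12 give 12 - 3 + 1 = 10 weekly calls. With 2 home visits, T2 and T3, that is 2 + 10 + 2 = 14 scheduled contacts per participant in every arm, plus the bi-monthly calls, whose number is not given. None is stated to include a question about events. Table 3 lists no adverse-event or hospitalisation measure.

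**4. Equality across arms.** Scheduled contact is the same in all arms, but the means of noticing and reporting are not. The Study Conditions section withholds self-monitoring equipment from attention control, and the call-the-nurse instruction sits in the walking-intervention text. The controls are nevertheless advised to exercise, and their stretching is taught by a nurse not involved with the other arms.

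**5. The treadmill.** These tests run under continuous ECG with staff present, and untoward changes go to the study cardiologist. Staff will see the event, so the only question there is whether it is classed as an adverse event.

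**6. Start of the reporting window.** The Procedures section randomises after baseline. A window that opened at randomisation would miss the baseline treadmill test. Table 3 schedules two such tests (baseline and 3 months), so one of two would be lost, or one of three if the Procedures wording means that the test is repeated at 6 months.

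**The case against.** The best defence is that the home instructions are emergency advice. They are silent on telling the study afterwards and do not forbid it. Counselling participants about home symptoms suggests that staff hear of them. The Acceptability paragraph has staff ask about barriers to adherence and perceived health improvements at visits and calls, without restriction by arm, and Table 3 includes a nurse telephone log. The detailed monitoring plan is deferred and may settle all of this.

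Much of that stands, and it rules out three stronger readings that a reader might infer:

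- *That these events would go uncounted.* The text does not show this. Contacts exist through which events could surface, and some routes to research staff are stated.
- *That most control-arm events would be missed.* This is not shown either. The Design section counts attention control among the intervention conditions, symptoms linked to an evaluation qualify in every arm, and scheduled contact is equal.
- *That a between-arm safety comparison would be biased.* No aim or analysis in the documents plans one.

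The defence does not remove the narrower point. The Acceptability topics and the adherence log are not event questions. The rule that all adverse events are reported applies only to what the definition admits and the study hears of. The monitoring section already supplies a definition that the later plan would inherit.

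**Conclusion.** The point holds in limited form. The definition is symptom-based and tied to the intervention or an evaluation. Serious events are undefined, and death and hospitalisation are not named as reportable. Shocks, emergency visits and hospitalisations at home may not be captured systematically or equally across arms, and so may not reach the DSMB.

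The size of any under-capture cannot be derived. About 90% of the preliminary cohort had an ICD, so the shock pathway is relevant to this population, but no shocks were reported in that work. The conclusion assumes that staff follow the text as written and that the deferred monitoring plan, which is not available here, does not already widen it. This is an inexpensive improvement to safety oversight. It is not evidence that the trial is unsafe.

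**What to change.** - **Definition.** Replace it with any untoward medical occurrence, symptomatic or not and whatever its cause, from consent or the first study procedure through the T3 visit. Record seriousness (including death, hospitalisation, emergency visit and ICD shock) and relatedness as separate items.
- **Collection.** Ask one identical short event checklist in all three arms at the existing home visits, calls, T2 and T3.
- **Home events.** Add a step to inform the research nurse afterwards, and leave every care step as it is. Reconcile the walking-risk text with the monitoring section on when the study is told.
- **DSMB.** Report counts by arm, and reconcile the unqualified mention of adverse events with the annual review's restriction to study-related ones.

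The monitoring section needs revision in any case: it refers to muscle strength testing and a resistance intervention that form no part of the design described elsewhere.

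The cost is revised wording, a short checklist and a few minutes per contact, with no added visits. The downside is that more unrelated events will be recorded in a sick population, which is why relatedness should be a separate item.
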